2. Community Health Workers (CHWs) will receive a \$25 gift card for completing focus groups. In addition, CHWs will receive an annual stipend that averages \$500 each year for three years for conducting the depression screening activities described herein.

3. Community members with a positive depression screen will receive gift cards worth up to \$65 for completing baseline, 3-, and 6-month assessments. In addition, a subset of community members will be randomly seleted to complete semi-structured interviews. Community members will receive a \$25 gift card for completing semi-structed interviews.

Alternatives:

If this research involves an intervention that presents greater than minimal risk to participants, describe available alternative interventions and provide data to support their efficacy and/or availability. Note, participants always have the option not to participate in research.

[] Abbreviated Submission - This information is included in an attached stand-alone protocol. Proceed to the next question

There are no alternatives to participation. Church members who decide not to participate or are ineligible for the RCT will be provided with mental health resources, if requested.

Page 20 of 25

Data and Safety Monitoring:

Describe how data and safety will be monitored locally and, if this is a multi-center study, how data and safety will be monitored across sites as well.

[] Abbreviated Submission - This information is included in an attached stand-alone protocol. Proceed to the next question

Data Safety Monitoring Plan. In compliance with NIH requirements, we will establish a data and safety monitoring plan (DSMP). The purpose of these plans is to ensure the safety of participants and the validity and integrity of the data. Considering the study rationale, population, procedures, and the risk: benefit profile as outlined; the overall risk level for participation in this screening intervention is classified as minimal. Due to the classification of this study as minimal risk, the following members of the investigative team will serve as the Data Safety Monitoring Committee and will perform the monitoring: [name], Contact-Principal Investigator (Columbia University, Dept. of Psychiatry). [name] will be responsible for corresponding with NIMH. In addition to providing timely reports to NIMH, regarding (i) Unanticipated problems or unexpected serious adverse events that may be related to the study protocol, (ii) IRB-approved revisions to the study protocol that indicate a change in risk for participants, and (iii) Notice of any actions taken by the IRB or regulatory bodies regarding the research and any responses to those actions, [name] will be responsible for: Reviewing all PHQ-9 questionnaires and assessments by participants students at baseline, 3-, and 6months; Reviewing safety plans documented by CHWs; and Reviewing rates of participant referral to treatment.[name], Multiple-Principal Investigator (Columbia University, Dept. of Neurology). [name] will provide site oversight by auditing CHW protocols and church sites where the intervention and control programs will take place. In addition to intervention fidelity monitoring, [name] will perform random interviews with CHWs (at least once at each church site) to evaluate the presence of any adverse reactions to the curriculum that may not be captured by questionnaire data. [name], Co-Investigator (Hebrew Home at Riverdale). [name] is the head project statistician at the Research Division of the Hebrew Home at Riverdale. She and her team will act as the Data Coordinating Center (DCC) and regularly review program data, which will be discussed with the MPIs monthly. These data will include guestionnaire items designed to capture adverse student emotional responses to the intervention. [name] has directed over 100 DCCs for single and multi-site projects, and has served on many DSMBs.Project Director – TBN. The Project Director will be present on site at every intervention and control program. In addition to project management activities such as recruitment, consenting, training, and data collection, the PD will be responsible for identifying and reporting any adverse encounters - related or unrelated to the intervention - to the Multi-PIs. These include adverse emotional responses, interpersonal conflicts, physical accidents or any other participant safety concerns that may occur during the intervention. Monitoring Study Safety: The data and safety monitoring plan will consist of reporting of adverse events to the IRB and to NIH trials. Adverse events will be reported to the Columbia IRB, which has the authority to halt the trial if it perceives that harm is occurring due to the intervention. Summaries of adverse events reports will be made to NIH in the yearly progress report and at the end of year 5, in the final report, unless the nature of a particular event is such that it bears reporting to NIH immediately. The progress of the trial will also be evaluated from the initial screening of participants by inclusion and exclusion criteria to the informed consent process to the provision of participant study instruction to staff training in Good Clinical Practices (GCP) and regulations pertaining to the Conduct of Human Participant Research. This will also include internal monthly quality control audits, periodic assessments of data quality and timeliness,

IRB-AAAT1474

Page 21 of 25

participant recruitment, accrual and retention, and protocol fidelity monitoring. One or more 'Early Safety/Trial Integrity Reviews' will be held during the early stage of protocol enrollment, to review early safety information, to review factors relating to quality of trial conduct, and to ensure proper implementation of procedures to reassess the sample size.

Subjects

Unless otherwise noted, the information entered in this section should reflect the number of subjects enrolled or accrued under the purview of Columbia researchers, whether at Columbia or elsewhere.

Target enrollment:

3,000

Number anticipated to be enrolled in the next approval period:

200

Does this study involve screening/assessment procedures to determine subject eligibility?

Yes

Target accrual:

600

Number anticipated to be accrued in the next approval period:

20

Is this a multi-center study?

No

Does this study have one or more components that apply to a subset of the overall study population (e.g. Phase 1/2, sub-studies)?

No

Target Enrollment Demographics:

Population Gender

Females 60%		Males 40%			Non Specific 0%	
Population Age)					
0-7 0%	8-17 0%	18 90	-65 %	>65 10%	Non 0%	Specific
Population Rac	e					
American Indian/Alaskan Native	Asian	Native Hawaiian or Other Pacific Islander	Black or African American	White	More than One Race	Non-Specific
0%	1%	0%	96%	3%	0%	0%

Population Ethnicity

Hispanic or Latino	Not Hispanic or Latino	Non-Specific
10%	90%	0%

Vulnerable Populations as per 45 CFR 46:

Will children/minors be enrolled

No

Will pregnant women/fetuses/neonates be targeted for enrollment?

No

Will prisoners be targeted for enrollment?

No

Other Vulnerable Populations:

- []Individuals lacking capacity to provide consent
- []CU/NYPH Employees/Residents/Fellows/Interns/Students
- [x]Economically disadvantaged
- []Educationally disadvantaged
- []Non-English speaking
- []Other Vulnerable populations
- []None of the Populations listed above will be targeted for Enrollment

Subject Population Justification:

Women: We will recruit women and men equally. Based on our previous studies, along with prevalence estimates of depression and demographics of Black churches, we anticipate that rates of recruitment for the present studies will be approximately 3:2 female to male. In our preliminary depression screening study that involved three Black churches in New York City, 56% of participants were women and 44% of participants were men

Minorities: We are not excluding based on race or ethnic background. Because the long-term goal of this study is to reduce the racial disparities in depression and the study settings are historically Black churches, we expect the majority participants in this study to self-identify as Black or Hispanic. In our preliminary depression screening study that involved three Black churches in New York City, 96% self-identified as Black/African American.

Children: This study is only for adults ages 18 years and older

Does this study involve compensation or reimbursement to subjects?

Yes

Describe and justify reimbursement/compensation:

1. Clergy will recieve a \$100 gift card for completing semi-structured interviews.

2. Community Health Workers (CHWs) will receive a \$25 gift card for completing focus groups. In addition, CHWs will receive an annual stipend that averages \$500 each year for three years for conducting the depression screening activities described herein.

3. Community members with a positive depression screen will receive gift cards worth up to \$65 for completing baseline, 3-, and 6-month assessments. In addition, a subset of community members will be randomly seleted to complete semi-structured interviews. Community members will receive a \$25 gift card for completing semi-structed interviews.

4. Each church study site will receive \$1,000 for use of church space to conduct study procedures. Are subjects eligible for compensation of \$600 or more in a calendar year? No

Attached Consent Forms

Number	Copied From	Form Type	Title	Active/InActive	Initiator
AABY9969		Consent	Commun ty Member	Act ve	[name]
IRB-AAAT1474	1	Page 23 of 25			mbia University IRB (Y1M0) oved for use until: 07/07/2021

Number	Copied From	Form Type	Title	Active/InActive	Initiator
			Depress on Screen ng		([name])

Documents

Archived	Document Identifier	Document Type	File Name	Active	Stamped	Date Attached	Created By
Yes	CHW Consent Form	Consent Form/Addendum	Consent Form CHW 6.17 .2020.pdf	Y	No	06/22/2020	[name] ([name])
No	Consent Form CHW	Consent Form/Addendum	Consent Form CHW 7.17 .2020.pdf	Y	Yes	07/20/2020	[name] ([name])
Yes	C ergy Consent Form	Consent Form/Addendum	Consent Form CLERGY 6.17.2020.pdf	Y	No	06/22/2020	[name] ([name])
No	Consent Form CLERGY	Consent Form/Addendum	Consent Form CLERGY 7.17.2020.pdf	Y	Yes	07/20/2020	[name] ([name])
Yes	Commun ty Member Consent Form	Consent Form/Addendum	Consent Form COMMUNI TY MEMBER 6.17.2 020.pdf	Y	No	06/22/2020	[name] ([name])
No	Consent Form COMMUNI TY MEMBER	Consent Form/Addendum	Consent Form COMMUNI TY MEMBER 7.17.2 020.pdf	Y	Yes	07/20/2020	[name] ([name])
No	CUIMC-IT Ema Ver f cat on	Ema /Commun c at on/Message	CUIMC-IT Ema Ver f cat on.pdf	Y	No	07/22/2020	[name] ([name])
No	Grant App cat on	Fund ng/Grant App cat on/Subc ontract	F na Spec f c A ms and Research Strategy.pdf	Y	No	06/17/2020	[name] ([name])
No	[name] CU Cert f cate.TC009 8.[name].202007 15	Other	[name] CU Cert f cate.TC009 8.[name].202007 15.pdf	Y	No	07/22/2020	[name] ([name])
No	Church Study S tes Letters of Support	Other	F na Letters of Support.pdf	Y	No	06/17/2020	[name] ([name])
No	Not ce of Grant Award	Other	[name] NIH N OA 1R01MH121 590-01A1.pdf	Y	No	06/17/2020	[name] ([name])
No	[name] CRC Tra n ng Cert f cate JM 7. 14.20	Other	[name] CRC Tra n ng Cert f cate JM 7. 14.20.pdf	Y	No	07/22/2020	[name] ([name])
No	[name] CITI Comp et on Report 07.17.20 20	Other	[name] CITI Comp et on Report 07.17.20 20.pdf	Y	No	07/22/2020	[name] ([name])
No	MEMO Respons e to IRB Rev ew 07.22.20 20	Other	MEMO Respons e to IRB Rev ew 07.22.20 20.pdf	Y	No	07/22/2020	[name] ([name])
No	[name] CITI Comp et on Report 07.15.20 20	Other	[name] CITI Comp et on Report 07.15.20 20.pdf	Y	No	07/22/2020	[name] ([name])
No	Part c pant Recru tment Ema Scr pt	Recru tment Mater a	Part c pant Recru tment EM AIL Scr pt 6.17.2020.pdf	Y	No	06/26/2020	[name] ([name])

Archived	Document Identifier	Document Type	File Name	Active	Stamped	Date Attached	Created By
No	Soc a Support	Study Mater a /Instrume nt	8 Item Soc a Support Survey 07.2020. pdf	Y	Yes	07/20/2020	[name] ([name])
No	CSSR-S	Study Mater a /Instrume nt	Br ef CSSRS- L fe ne-Vers on- 2014.pdf	Y	Yes	07/22/2020	[name] ([name])
No	Char son	Study Mater a /Instrume nt	Char son Comorb d ty Index 07.2020.p df	Y	Yes	07/20/2020	[name] ([name])
No	CPIC Hea th Serv ces	Study Mater a /Instrume nt	CPIC Hea th Serv ces 07.202 0.pdf	Y	Yes	07/20/2020	[name] ([name])
No	Demograph cs	Study Mater a /Instrume nt	Demograph cs 0 7.2020.pdf	Y	No	07/20/2020	[name] ([name])
No	Depress on St gma	Study Mater a /Instrume nt	Depress on St gma and L teracy 07.2020 .pdf	Y	Yes	07/20/2020	[name] ([name])
No	CHW Interv ew Gu de	Study Mater a /Instrume nt	F na CFIR CHWs Interv ew 11.1.19.pdf	Y	Yes	06/17/2020	[name] ([name])
No	Commun ty Member Interv ew Gu de	Study Mater a /Instrume nt	F na CFIR Subjects Screened 11.1.19.pdf	Y	Yes	06/17/2020	[name] ([name])
Yes	CPIC Hea th Serv ces	Study Mater a /Instrume nt	F na CPIC Hea th Serv ces 11.1.19 .pdf	Y	No	06/17/2020	[name] ([name])
Yes	MHP Appo ntment Ver fcat on Form	Study Mater a /Instrume nt	F na MHPAAV Form 11.2.19.pdf	Y	No	06/17/2020	[name] ([name])
No	C ergy Interv ew Gu de	Study Mater a /Instrume nt	F na CFIR C ergy Interv ews 11.1.2019.pdf	Y	Yes	06/17/2020	[name] ([name])
No	MHP Appo ntment Ver f cat on Form	Study Mater a /Instrume nt	MHPAAV Form 07.2020.pd f	Y	No	07/20/2020	[name] ([name])
No	NYP Referra Gu de	Study Mater a /Instrume nt	NYP Menta H th D r UNSTAMPED 08.29.17.pdf	Y	No	06/17/2020	[name] ([name])
No	PHQ9 V sua A d	Study Mater a /Instrume nt	PHQ9 V sua Answer A d ENGLISH.pdf	Y	Yes	06/17/2020	[name] ([name])
No	PHQ9	Study Mater a /Instrume nt	PHQ9 07.2020.p df	Y	Yes	07/20/2020	[name] ([name])
No	PROMIS 8a Depress on	Study Mater a /Instrume nt	PROMIS SF v1. 0 - ED- Depress on 8a 0 7.2020.pdf	Y	Yes	07/20/2020	[name] ([name])
No	PTSD 5	Study Mater a /Instrume nt	PTSD5- screen 07.2020. pdf	Y	Yes	07/20/2020	[name] ([name])
No	QIDS 16	Study Mater a /Instrume nt	QIDS16-Se f Report Eng sh.pdf	Y	Yes	07/20/2020	[name] ([name])
No	Re g ous H story	Study Mater a /Instrume nt	Re g ous and Sp r tua H story 07.2020. pdf	Y	Yes	07/20/2020	[name] ([name])
No	Short Form 12	Study Mater a /Instrume nt	Short Form 12 07.2020.pdf	Y	Yes	07/20/2020	[name] ([name])
No	S tuat ona Mot vat on Sca e	Study Mater a /Instrume nt	S tuat ona Mot vat on Sca e 07.2020.p df	Y	Yes	07/20/2020	[name] ([name])
No	Stan ey-Brown Safety P an	Study Mater a /Instrume nt	Stan ey-Brown SAFETY PLAN 02.2019.p df	Y	Yes	06/17/2020	[name] ([name])

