Each CHW will collaborate with church leaders (see study sites and letters of support) to organize depression screening events at church health-focused programs. Two CHWs and at least one Project Coordinator (PC) will be present at the church for each screening event to assist with scoring the Patient Health Questionnaire-9 (PHQ-9), interpreting the results, and study enrollment. Eligibility for depression screening include: 1) Adults 18 years and older; and 2) English-speaking. There are no exclusion criteria for general depression screening. The screening will occur in a private space in the church to protect participant confidentiality. The screening survey will include the PHQ-9 and demographic information. Participants will submit their completed survey to the CHW in a private church space, who will quickly assess for suicidality by examining responses to Question #9 of the PHQ-9. Eligibility for the Randomized Controlled Trial (RCT) depends on the participants' total PHQ-9 score:

- Participants whose PHQ-9 9 (negative depression screen), are ineligible for the RCT and will receive a copy of Mental Health Resources.

- Participants whose PHQ-9 10 (positive depression screen), will be eligible for the RCT and invited to sign informed consent to participate in the study.

Page 12 of 25

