Intervention arm: [(Screening + Brief Intervention + Referral to Treatment), n=15 churches]. CHWs will provide two Motivational Interviewing (MI) sessions in each of the first three months, for a maximum of 6-MI sessions over 3 months (Table 1). The initial two sessions will be conducted in person at the church and follow-up sessions will occur either in-church or over the phone. Data will be collected on method of delivery. MI sessions will create a nonjudgmental and supportive environment for eligible participants to move through the various stages of change associated with depression help-seeking. In the initial session, CHWs will focus on establishing rapport using openended guestions, affirmations, reflections, and summary statements (OARS). They will then review depression symptoms based on the participants PHQ-9 score. The second session will focus on assessing motivation and confidence in seeking treatment and elicit barriers and facilitators for depression treatment. Follow-up sessions will involve summarizing the 'pros' and 'cons' of depression treatment; providing options for the participant based on the nature of barriers elicited from them; assessing participant's values and goals, to help them link their current mental health pattern to their goals; and summarizing what was discussed to clarify an action plan. The final component of SBIRT involves actual referrals to treatment. This begins with determination of the individual's health insurance status. Persons without insurance will be enrolled with the assistance of CHWs (who are certified New York State Insurance Navigators) into New York State health plans (insurance exchange or Medicaid). Based on our preliminary studies, we expect 12 to 15% of subjects to be uninsured. Individuals ineligible for health insurance will be referred to our network of free clinics providing mental health services. Uninsured individuals will also be referred to the NYC Dept. of Health Action Centers, to insurance information, and other social services (see Letters of Support). Referral involves the CHW calling (using study-issued prepaid calling cards) or offering to call the provider's office on behalf of the subject to make an appointment, plus a follow up appointment call reminder the day before the appointment.

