Usual Care arm: [Referral as Usual (RAU), n=15 churches]. Distributing depression educational materials and contact information for treatment providers is the most common form of referral. This practice will represent "usual care" for our study. We will utilize depression educational brochures describing the nine hallmark symptoms of depression symptoms and the importance of seeking treatment: one from the National Institute of Mental Health (NIMH), one from the American Psychiatric Association (APA), and one from National Alliance of Mental Illness (NAMI). CHWs assigned to usual care churches will distribute the list of referral sites and pamphlets to study participants at designated

screening events. No specific referrals will be made in this arm.

Page 13 of 25

Assessments. Within two weeks of completing the PHQ-9 and study enrollment, Project Coordinators will conduct telephone baseline assessments with participants who signed informed consent. Table 3 shows the name and construct for each clinical measure collected at baseline, 3-months, and 6-months post screening.

VIRTUAL STUDY PROCEDURES

Considering COVID-19 and the New York State on Pause law, we will also conduct study procedures virtually. Study Project Coordinators will facilitate Columbia-HIPPA compliant Zoom screening events with church members from approved church study sites. The same study procedures outlined above will be followed, however, the interaction will be conducted via Zoom.

Recruitment And Consent

Recruitment:

Will you obtain information or biospecimens for purposes of screening or determining eligibility? No

Describe how participants will be recruited:

This study involves three distinct study populations.

(1) Clergy (n=30): The lead pastor of each church study site will be recruited for participation in a semi-structured interview. The purpose of the interview is to explore clergy's perspectives of church-based depression screening and awareness of CHW activities in their church. Clergy will received a \$100 gift card as compensation in the interview.

(2) Community Health Workers (n=60): CHWs form Columbia's Training Program will be eligible for participation in focus groups. The purpose of the focus groups is to identify barriers and facilitators of SBIRT (intervention) implementation and factors that would contribute to long-term sustainability of the intervention in churches. CHWs will receive \$25 for participation in focus groups

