(3) Community Members (n=600): CHWs, Project Coordinators, and Research Assistants will be present at church study sites to obtain written consent from eligible adults who screen positive for depression (PHQ-9 greater than 10). Consent procedures will occur in a private area of the church to protect patient confidentiality

[] Informed consent will be obtained but a waiver of written documentation of consent (i.e., agreement to participate in the research without a signature on a consent document) is requested.

Page 15 of 25

[x] A waiver of some or all elements of informed consent (45 CFR 46.116) is requested.

Waiver of consent is applicable to:

A portion of the study or subject population

Identify the portion of the study (e.g., retrospective chart review portion of the study) or subject population where a waiver of consent applies:

We request a waiver of consent for depression screening procedures with the PHQ-9

Select the applicable situation:

[x]This study qualifies for a waiver or alteration of consent as the following criteria are met in this study (provide justification for EACH of these criteria):

(1)The research involves no more than minimal risk to the subjects Provide justification:

The PHQ-9 is a widely used, brief, self report measure that takes approximately 3 to 5 minutes to complete. We received waiver of consent on NYSPI IRB #6368 to conduct church-based depression screening with the PHQ-9.

(2) The waiver or alteration will not adversely affect the rights and welfare of the subjects Provide justification:

The PHQ-9 is a screening measure and will not impact the welfare of subjects. If a patient expresses suicidal ideation on the PHQ-9, we will follow the Safety Procedures outlined in the previous section and initiate more in-depth assessment of suicidality with the Columbia-Suicide Severity Rating Scale

(3) The research could not practicably be carried out without the waiver or alteration Provide justification:

It would be impractical and overly time consuming to try to obtain consent prior to screening with the PHQ-9. Only adults with a positive depression screen (PHQ-9 greater than 10), will be eligible for the RCT and will be required to provide informed consent to participate in the RCT

(4) Whenever appropriate, the subjects will be provided with additional pertinent information after participation

Provide justification:

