health services for depression. Indeed, in the first study of its kind, the study team found that 20% of adults in Black churches screened positive for depression using the Patient Health Questionnaire-9 (PHQ-9). However, no subjects with a positive screen (PHQ-9 10) accepted a treatment referral when offered by research coordinators onsite for each screening. Community Health Workers (CHWs), who are trusted para-professionals from the target community, may bridge the gap between depression screening and treatment. We have trained and certified 102 CHWs from 42 Black churches in Harlem to deliver an evidence-based intervention called Screening, Brief Intervention, and Referral to Treatment (SBIRT), which is centered on culturally tailored Motivational Interviewing (MI). Thus, the scientific premise of this study is that employing CHWs to implement depression screening in Black churches will bridge the gap between churchbased depression-screening and engagement with clinical providers. Using a Hybrid Type 1 Effectiveness-Implementation design, we propose a 2-arm, mixed-methods Cluster-Randomized Controlled Trial within 30 Black churches our CHWs currently attend. Based on our pilot data, we expect 20% of adults (n=600) to have a positive depression screen. Adults will be randomized based on church study site to either SBIRT (n=15 churches) or Referral As Usual (RAU, n=15 churches). We will then compare the effectiveness of SBIRT (Intervention arm) to RAU (Usual Care arm) on treatment engagement (primary outcome), defined as attending a depression-related clinical visit for which the subject reported receiving information, referral, counseling, or medication for depression (Aim 1). We will then compare changes in Mental Health Related Quality of Life and depressive symptoms (secondary outcomes) at 3- and 6-months post-screening (Aim 2). Finally, we will conduct a concurrent, mixed-methods (qualitative-quantitative) process evaluation to assess contextual facilitators and barriers of screening and referral (Aim 3). This study has potential for large-scale public health impact as 20 to 22 million Americans attend the 65,000 to 70,000 Black churches in the U.S.

Lay Abstract:

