[] Abbreviated Submission - This information is included in an attached stand-alone protocol. Proceed to the next question

We expect the level of risk due to this intervention to be minimal as no invasive measures or procedures are proposed. However, given the target sample, patients may experience distress as they are asked questions about depressive symptoms and other assessments. It is possible that some patients may find the frequency of calls and visits to be excessive. There is a potential risk to the participant with regards to possible violation of the participant's privacy since survey responses will be used as a source of data. Two CHWs and at least one Project Coordinator (PC) will be present for each depression screening event at designated church study sites. The CHWs will focus on reviewing PHQ-9 scores with community members. The PC(s) will focus on consenting eligible adults who screen positive for the Randomized Controlled Trial. When the prospective participant has completed the PHQ-9, the CHW and PC will briefly calculate their total PHQ-9 score and assess for suicidality. Individuals who score 10 on the PHQ-9 will be contacted within 14 days to schedule a baseline assessment and verify study eligibility. A telephone interview assessment will then be scheduled for those who agree. At the start of this interview, the interviewer will obtain informed consent from the patient. The consent will include permission to contact the participant's treatment facility where they seek depression treatment, obtain selected data from the patients' other health care providers, and share information with our CUIMC collaborators. All participants will be informed that they can refuse to answer questions, stop the assessment at any time, or withdraw from the study if they so wish, without in any way affecting their eligibility or receipt of usual health or social services. Every effort will be made to streamline the interview and make it as comfortable as possible. Safety Assessment During Screening and Study Procedures. We have developed a comprehensive safety plan that will be activated if a research participant endorses suicidal ideation either verbally or on the PHQ-9 (included in IRB #6368). First, the CHW will screen for suicidality with the Columbia-Suicide Severity Rating Scale (C-SSRS). This measure to was designed to quantify the risk and intent of suicidal ideation / behavior. Second, the CHW will immediately contact the on-call clinician, who will conduct a standardized clinical assessment to evaluate immediacy of suicidal risk. If the research participant has active suicidal ideation/behavior, the on-call clinician will refer the participant to immediate clinical care by either calling 911 (if the patient consents for treatment) or Mobile Crisis (if the participant refuses to go to the emergency room). If the research participant does not have active suicidal ideation/behavior, the on-call clinician will refer the participant for an in-person clinical assessment with a licensed clinician on the research study team within 48 hours. If the participant

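### Community Health Workers who know and deliver their church's arm help enrol and consent participants after allocation, and the protocol contradicts itself on who takes consent and when

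*Protocol*

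**What the plan says.** **Allocation.** The Scientific Abstract fixes each person's arm by church: "Adults will be randomized based on church study site to either SBIRT (n=15 churches) or Referral As Usual (RAU, n=15 churches".

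**CHWs know and deliver the arm.** Under Intervention arm, "CHWs will provide two Motivational Interviewing (MI) sessions in each of the first three months", and they also make the referral calls. Under Usual Care arm, "CHWs assigned to usual care churches will distribute the list of referral sites and pamphlets to study participants", and this happens at the screening events.

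**CHWs also recruit.** Church-Based Study Procedures puts two CHWs and at least one Project Coordinator (PC) at each event "to assist with scoring the Patient Health Questionnaire-9 (PHQ-9), interpreting the results, and study enrollment". Under Informed Consent Process, the item on community members reads: "CHWs, Project Coordinators, and Research Assistants will be present at church study sites to obtain written consent from eligible adults who screen positive".

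**Other accounts of consent.** Potential Risks states: "The PC(s) will focus on consenting eligible adults who screen positive for the Randomized Controlled Trial". The same section then has the interviewer obtain consent at the start of the telephone baseline interview. The Assessments paragraph says that those telephoned have already signed. Data and Safety Monitoring lists consenting among the tasks of the Project Director, who is on site at every intervention and control program.

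Nothing in the protocol says that a recruiter is unaware of the church's arm, or that consent precedes allocation.

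**The concern.** In a cluster trial, randomisation balances the churches. It balances the participants only if finding, inviting and consenting them does not depend on the arm. Here people seem to be identified and consented after their church is allocated, with help from staff who know what that church offers. A CHW in an SBIRT church can offer up to six motivational interviewing (MI) sessions and help with an appointment. A CHW in a usual-care church can offer a list and pamphlets. How warmly people are invited, and who accepts, can therefore differ by arm.

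The trait at risk is willingness to seek care, which is close to the primary outcome. In the pilot no screen-positive person accepted a referral, so modest differences in the mix of willing and unwilling people could shift engagement. Part of the observed difference would then be selection, or selection would hide part of a true effect. Adjusting for PHQ-9 severity would not remove a difference in willingness.

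**Working it through.** **1. Is the arm known at recruitment?** The protocol does not date randomisation. But CHWs described as already assigned to usual-care churches distribute control materials at the screening events, which is where enrolment takes place. Allocation before recruitment is a strong inference, not a stated fact.

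**2. Who consents, and when?**

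| Section | Who | When |
|---|---|---|
| Church-Based Study Procedures | CHWs and PC assist with enrolment | at the event |
| Informed Consent Process | CHWs, PCs and research assistants | at the church |
| Potential Risks, first statement | PCs focus on this | at the event |
| Potential Risks, second statement | interviewer | start of telephone baseline |
| Assessments | not named | already signed before the telephone baseline |
| Data and Safety Monitoring | Project Director, among other duties | not stated |

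These cannot all hold. None of them removes knowledge of the arm.

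**3. Planned size (Statistical Procedures).** 30 × 100 = 3,000 screened; 20% positive gives 600, so 20 per church and 300 per arm. This reproduces. The planned difference is 10 to 11 points.

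**4. Illustration with no treatment effect.** All rates are assumptions: 30% of positives are ready and 30% of these engage; 70% are not ready and 5% of these engage. Usual care consents 60% of both groups. SBIRT consents a share c1 of the ready and c2 of the rest.

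- Ready share s = 0.3·c1 / (0.3·c1 + 0.7·c2)
- Engagement = 0.30·s + 0.05·(1 − s)
- Usual care: s = 0.30, engagement p0 = 0.125

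| c1, c2 | s | SBIRT engagement p1 | Bias (points) |
|---|---|---|---|
| 0.8, 0.6 | 0.364 | 0.141 | +1.6 |
| 0.8, 0.5 | 0.407 | 0.152 | +2.7 |
| 0.8, 0.4 | 0.462 | 0.165 | +4.0 |
| 0.8, 0.8 | 0.300 | 0.125 | 0 |
| 0.6, 0.8 | 0.243 | 0.111 | −1.4 |

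**5. Type I error in the three positive cases.** Assume a two-sided 5% test and ICC 0.01. With r = bias/SE, the rejection rate is Φ(r − 1.96) + Φ(−r − 1.96).

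- *300 analysed per arm.* Design effect 1 + 19 × 0.01 = 1.19; SE = √{[p0(1 − p0) + p1(1 − p1)] × 1.19/300}. r = 0.53, 0.87, 1.29, giving 8%, 14% and 25%.
- *600 as all screen-positives, before consent.* Usual care then has 300 × 0.60 = 180. SBIRT has 300 × (0.3·c1 + 0.7·c2) = 198, 177 or 156. With about 10 to 13 per church the design effect is about 1.1, giving about 7%, 11% and 17%.

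**6. Sensitivity.** With other assumed inputs (50% ready, engagement 50% and 10%, 80% consent in usual care), SBIRT consent of 80% and 40% gives s = 0.667 and 0.10 + 0.40 × 0.667 = 0.367 against 0.300, or +6.7 points. SBIRT consent of 60% and 80% gives s = 0.429 and 0.271, or −2.9 points.

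**The case against.** **Potential Risks divides the work.** It has CHWs review scores and PCs consent, and the enrolment sentence can be read as describing a team. This has force for that sentence, but the consent section still names CHWs outright. A reader might infer that Potential Risks reserves consent to the PC alone. It does not: it also has the telephone interviewer take consent, and it has the CHW and PC total the PHQ-9 together.

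**Scoring is a weak route to bias.** A reader might infer that CHWs could tilt eligibility through the score. The PHQ-9 is self-report with a fixed cut, so there is little room for that. The exposure is in invitation and consent.

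**The direction is unknown.** A reader might infer that the bias favours SBIRT. The document does not support this. The two larger positive cases need SBIRT to consent fewer of the not-ready than usual care, which a richer offer does not explain. CHWs trained in MI may equally win over reluctant people, which gives the negative case.

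**Partial safeguards exist.** The document list includes a situational motivation scale and a depression stigma and literacy measure, so PHQ-9 is not the only possible covariate; when they are collected cannot be seen. Data and Safety Monitoring provides for review of screening, consent and accrual. These help to detect or partly adjust for a difference. They do not prevent one.

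**CHW-led screening is the study's premise**, and in the pilot referrals offered by research coordinators were declined. This stands as a reason to leave screening with CHWs. It concerns acceptance of treatment referral, and does not require CHWs to take research consent.

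**Conclusion.** The concern holds in limited form. Staff who know and deliver the arm have a stated part in enrolment and consent after what appears to be prior allocation, no safeguard is described, and the sections disagree on who takes consent and when. This is a matter of design and wording, which a later analysis plan cannot fully repair.

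The protocol supports neither a direction nor a size. The range of −1.4 to +4 points, and type I error of about 8 to 25% (or about 7 to 17% with fewer consenting), rest wholly on assumed readiness, engagement and consent rates and an assumed ICC. They show that a plausible imbalance could matter against a 10 to 11 point target, and do not show that one will occur. A reader might also infer that the stated power is wrong. Nothing here bears on that: its inputs are in an attachment that is not shown. The change should be made; confidence is medium.

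**What to change.** 1. Reconcile Church-Based Study Procedures, Assessments, Informed Consent Process, Potential Risks, and Data and Safety Monitoring, so that they give one account of who takes consent and when.
2. In all 30 churches, have only the PC or a research assistant invite screen-positive people and obtain consent, using one arm-neutral script, before any arm-specific material or MI is offered.
3. Leave CHWs organising and conducting screening, reviewing scores and carrying out their safety role. They need not be barred from totalling the PHQ-9.
4. Log screen-positive, eligible, invited and consented numbers per church, and report them by arm.

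The safeguard should not depend on keeping the PC unaware of the arm, which is doubtful when control materials are handed out at the same event. The script and the order of steps do the work.

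The cost is protocol wording, one script and one log. A PC is already due at every event, and the planned 600 and the power inputs do not change. The downside is less CHW help with sign-up. The change does not control who attends an event that a CHW has organised, though the log would show part of that.
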